8.2 Determination of Sample Size and Accrual Rate

8.2.1 Sample Size and Power Estimate

The primary endpoint is to evaluate the positive predictive value (PPV) on a (1) per-patient and (2) per-region-basis (prostate bed, pelvis, extrapelvic soft tissue, and bone metastases) of ⁶⁸Ga-PSMA-11 PET for detection of tumor location confirmed by histopathology/biopsy. Based on the results of previous studies, the following distribution of disease across the four regions are anticipated (19-21):

- a) Prostate bed: 30%
- b) Pelvis: 15%
- c) Extrapelvic soft tissue: 20%
- d) Bone metastases: 35%

It is anticipated that the PPV for the four regions and for all regions combined using conventional imaging ranges from 30-60%. An overall PPV for ⁶⁸Ga-PSMA-11 PET of at most 50% will be considered as unacceptably low. Hence, the null hypothesis that the PPV is at most 50% will be tested against the alternative hypothesis that the PPV is greater than 50%. It is hypothesized that ⁶⁸Ga-PSMA-11 PET imaging on the per-region and per-patient basis will substantially increase the PPV for the four regions to at least 70%. A sample size of 75 true positives is required for rejecting the null hypothesis that the PPV is at most 50% with 90% power at the one-sided 0.01 (=0.05/5 – a Bonferroni adjustment for evaluating the PPV for the four regions and for all regions combined) significance level, assuming an average regions specific prevalence of 20%. It is expected that approximately 25% of the accrued patients will undergo a biopsy. Hence, the proposed total number of patients requiring a biopsy is 375 in

order to power the analysis at a per region level. Assuming a prevalence rate of 20% for disease in each individual region, a total sample size of 1,500 patients is required. The following table shows the attainable power levels for detecting an increase in the PPV from 50% to 70% at the one-sided 0.01 significance level for the four disease regions and for all regions combined with the proposed sample size of 1500 patients:

Table: *Attainable power levels for detecting an increase in PPV from 50% to 70% with sample size of 1,500 patients (375 biopsies)*

	Prevalence	Number of Biopsies with True Positives	Power
Prostate bed	30%	113	98%
Pelvis	15%	56	78%
Extrapelvic soft tissue	20%	75	90%
Bone metastases	35%	131	>99%
All regions combined	100%	375	>99%

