^{68}Ga -PSMA-11 PET positive findings will be validated as true or false positive as outlined in more detail below. False negative ^{68}Ga -PSMA-11 PET findings cannot be determined as this would require biopsies of ^{68}Ga -PSMA-11 negative but conventional or functional non- ^{68}Ga -PSMA-11 PET positive imaging lesions. Inclusion of such patients however would be violation of the inclusion criteria.

^{68}Ga -PSMA-11 PET validation based on follow-up imaging:

- i) Lymph nodes will be assessed by change in size. ^{68}Ga -PSMA-11 positive lymph nodes will be considered:
 - (1) True positive:
 - If on follow-up imaging within 3-12 months, lymph nodes seen on CT or MRI decrease by more than 30% (for patients undergoing systemic treatment of focal therapy at this site) or increase by more than 20% in short axis diameter (with a minimum of 3 mm in change in size).
 - If patients with solitary lymph node regions show a decrease of PSA by greater than 50% after targeted treatment (i.e. external beam radiation) and the lymph nodes do not change in size (less than 30% decrease or less than 20% increase in short axis diameter).
 - (2) False positive:

- If on follow-up imaging within 3-12 months, sites of initial⁶⁸Ga-PSMA-11 positive lymph node lesions seen on CT or MRI decrease by more than 30% *without* systemic therapy or focal therapy at this site.
 - If ⁶⁸Ga-PSMA-11 positive lymph node lesions do not meet the criteria for above false positive or true positive findings.
- ii) Visceral lesions (non-lymph node soft tissue or organ) will be assessed by change in size. ⁶⁸Ga-PSMA-11 positive visceral lesions will be considered:
- (1) True positive:
- If on follow-up imaging within 3-12 months, visceral lesions seen on CT or MRI decrease by 30% (for patients undergoing systemic treatment of focal therapy at this site) or increase by 20% in largest diameter.
 - If patients with solitary visceral metastasis show a decrease of PSA by greater than 50% after targeted treatment (i.e. external beam radiation) and lesions do not change in size (less than 30% decrease or 20% increase in largest diameter).
- (2) False positive:
- If on follow-up imaging within 3-12 months, sites of initial⁶⁸Ga-PSMA-11 positive lymph node lesions seen on CT or MRI decrease by more than 30% *without* systemic therapy or focal therapy at this site.
 - If ⁶⁸Ga-PSMA-11 positive lymph node lesions do not meet the criteria for above false positive or true positive findings.

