- iii) ⁶⁸Ga-PSMA-11 positive bone lesions will be considered:
- (1) True positive:
- If there was a corresponding positive sclerotic lesion on the CT portion of the ⁶⁸Ga-PSMA-11 PET.
 - If there is focal uptake seen on the baseline bone scan performed within one month of ⁶⁸Ga-PSMA-11 PET.
 - If there is a lesion noted on the initial MRI performed within one month of ⁶⁸Ga-PSMA-11 PET.
 - If within 12 months follow-up CT demonstrates development of sclerosis.
 - If within 12 months follow-up MRI demonstrates a new bone lesion.
 - If within 12 months follow-up bone scan demonstrates new focal uptake.
- (2) False positive:
- If ⁶⁸Ga-PSMA-11 positive bone lesions do not meet the criteria for true positive findings.
- iv) ⁶⁸Ga-PSMA-11 positive prostate bed and prostate lesions will be considered:

(1) True positive:

- If on follow-up imaging within 12 months, lesions seen on CT or MRI decrease by 30% (for patients undergoing systemic treatment of focal therapy at this site) or increase by 20% in largest diameter..
- If patients with prostate bed lesions show a decrease of PSA by greater than 50% after targeted treatment (i.e. external beam radiation) and lesions do not change in size (less than 30% decrease or 20% increase in largest diameter).

(2) False positive:

- If on follow-up imaging within 3-12 months, sites of initial⁶⁸Ga-PSMA-11 positive lymph node lesions seen on CT or MRI decrease by more than 30% *without* systemic therapy or focal therapy at this site.
- If ⁶⁸Ga-PSMA-11 positive lymph node lesions do not meet the criteria for above false positive or true positive findings.

c) Histopathology/Biopsy:

- i) Localization of lesions for histopathology/biopsy will be classified according to the regions in table 1.
- ii) ⁶⁸Ga-PSMA-11 positive findings are aimed to be confirmed by histopathology/biopsy if clinically feasible.
- iii) Histopathological procedures and biopsies will be performed as clinically indicated and as per institutional protocol.

(1) Positive HP/Biopsy: Confirmed sites of metastatic or tumor involvement by histopathology/biopsy will be discussed with the responsible physician/surgeon.

(2) Negative Biopsy: Patients with suspected tumor recurrence on ⁶⁸Ga-PSMA-11 PET with negative histopathology/biopsy will be handled as outlined below:

(a) Lymph nodes:

- For patients undergoing nodal dissection: Patients will be rescanned with dedicated CT or MRI to determine if the suspicious ⁶⁸Ga-PSMA-11 positive node was removed.

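### A bone lesion seen only on PSMA PET that is treated and never shows a later correlate is scored false positive, because the bone rule lacks the treatment-response routes given to the other lesion types

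*Combined protocol and SAP*

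**What the plan says.** Section 8.3.2 b) classifies PET-positive findings by imaging follow-up, with separate rules for four lesion types.

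- **Nodes (i), viscera (ii), prostate bed (iv).** Each has two treatment-response routes to true positive. One is a size decrease of about 30% under treatment. The other is a PSA response with stable size; for nodes it reads "If patients with solitary lymph node regions show a decrease of PSA by greater than 50% after targeted treatment (i.e. external beam radiation"). The visceral entry has the same PSA route for a solitary metastasis. The prostate-bed entry has it without the word solitary.
- **Bone (iii).** There are six routes. Three rest on findings at or near the PET: a sclerotic correlate on the PET/CT, or a bone-scan or MRI finding within one month. Three rest on follow-up: sclerosis developing on CT, "If within 12 months follow-up MRI demonstrates a new bone lesion", and "If within 12 months follow-up bone scan demonstrates new focal uptake". None is a shrinkage or PSA response. A finding is false positive if "positive bone lesions do not meet the criteria for true positive findings". There is no non-evaluable class.

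Section 8.3.2 b) also says that follow-up should use the same modalities as the initial work-up. Section 8.3.2 c) sends bone biopsies with indeterminate pathology back to these imaging rules. Section 8.3.1 restricts the primary analysis to patients with histopathology. Section 8.3.3 uses the imaging rules for the secondary PPV.

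**The concern.** Once the baseline correlates are absent, a bone lesion can be confirmed by imaging only if something new appears. Effective treatment can prevent a new MRI lesion or new uptake. Sclerosis can still confirm a treated lesion, but only if follow-up includes CT, which the matching of modalities does not guarantee.

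A solitary bone lesion irradiated on the PET result, with a PSA fall above 50% and no new correlate, is then false positive. A solitary nodal region with the same PSA course and stable size is true positive. The plan gives no reason for the difference.

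The error falls on bone lesions that conventional imaging did not show at baseline, which are the added yield that the trial wants to document. Treatment between PET and follow-up is foreseeable, because change in management is itself a secondary endpoint. Bone is also the largest expected disease region, at 35% (section 8.2.1).

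**Working it through.** **1. The rules side by side, for a true lesion seen only on PET, unbiopsied, solitary, and given targeted treatment after PET; PSA falls by more than 50%**

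| Course on follow-up | Node | Bone |
|---|---|---|
| Shrinks by more than 30% | True positive | No such route |
| Stable size, or no new correlate | True positive (PSA route) | False positive (default) |
| Sclerosis on CT | Not applicable | True positive |
| New MRI lesion or new uptake | Not applicable | True positive |

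The two types diverge in the second row. With a baseline correlate or a positive biopsy, the bone lesion would be true positive whatever happened later.

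**2. The plan's own figures**

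The plan states no figure for misclassification. The nearest figures are those of the PPV test in section 8.2.1.

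- Null: "the null hypothesis that the PPV is at most 50% will be tested against the alternative hypothesis", so p0 = 0.50.
- Alternative: PET "will substantially increase the PPV for the four regions to at least 70"%, so p1 = 0.70.
- Error rates: "with 90% power at the one-sided 0.01 (=0.05/5"), so z = 2.326 and 1.282.
- Stated size: "A sample size of 75 true positives is required for rejecting the null hypothesis".

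n = [(2.326 × √(0.5 × 0.5) + 1.282 × √(0.7 × 0.3)) / 0.2]² = 76.6, or 77 against the stated 75.

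Power = Φ{(p1 − p0 − 2.326 × √(0.25/n)) / √(p1(1 − p1)/n)}. For bone, n = 0.35 × 375 = 131, which gives 99.3% (stated: above 99%). The plan's figures are reproduced closely.

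**3. Effect of the bone rule**

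Let f be the share of true bone lesions scored false positive through this gap. The documents give no value, so f is an assumption. A misclassified lesion stays in the denominator, so scored PPV = 0.70 × (1 − f).

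| f (assumed) | Scored bone PPV | Power at n = 131, for scale only |
|---|---|---|
| 0% | 70.0% | 99.3% |
| 5% | 66.5% | 93.8% |
| 10% | 63.0% | 74.9% |
| 15% | 59.5% | 43.9% |
| 20% | 56.0% | 16.9% |

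The scored PPV reaches the null value of 50% at f = 1 − 0.50/0.70 = 28.6%.

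The last column only conveys scale. The 131 are biopsies planned for the primary PPV, and the imaging rule does not classify most of them.

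If bone made up 35% of the PET-positive regions validated (a further assumption, since the 35% is an expected distribution of disease), the all-region PPV would fall by 0.35 × 3.5 = 1.2 points at f = 5% and by 0.35 × 14 = 4.9 points at f = 20%. The per-patient effect would be smaller wherever another region is confirmed in the same patient.

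**4. Would excluding the affected lesions be better?**

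Take 100 bone lesions, 70 true and 30 false. Exclude the 14 true lesions affected at f = 20% and, as an assumption, half of the 30 false ones because they too were treated on the PET result. PPV = 56 / (56 + 15) = 56/71 = 79%, above the true 70%. Exclusion replaces a downward bias with an upward one, because a treated bone lesion could then never be false positive under the imaging rule.

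**The case against.** - **The gap is narrow.** A reader might infer that any bone metastasis treated successfully after PET is scored false positive. The text does not say so. A baseline CT, bone-scan or MRI correlate, sclerosis on later CT, or a positive biopsy each keeps a treated lesion true positive. This stands, and it limits the point to lesions with none of these.
- **The primary is largely untouched.** It rests on histopathology, and only indeterminate bone biopsies bring the imaging rule into it. This stands.
- **Bone also has advantages.** Its three baseline routes need no change over time, whereas the other types must change in size or show a PSA response. A reader might infer that bone PPV is biased low relative to the other regions; the documents do not establish that net direction. What remains is the downward error in the specific lesions described.
- **Nodes have a residual default too.** A treated node of stable size is also false positive if nodal disease is not solitary or if treatment was systemic only. This stands, but the nodal default applies after response routes that bone lacks.
- **The modality restriction is soft.** The plan says that follow-up modalities should match and allows CT, MRI and/or bone scan, so CT may be available. This lowers the likely size of the gap without closing it.

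**Conclusion.** The point holds in this limited form. A bone lesion seen only on PSMA PET, not confirmed by biopsy, treated after PET and never showing sclerosis, a new MRI lesion or new uptake is scored false positive even after a PSA fall above 50% following targeted treatment. This biases the bone part of the secondary PPV downward. Its size cannot be read from the documents: with a true bone PPV of 70% and an assumed 5% to 20% of true bone lesions affected, the scored value is 66.5% to 56%. The documents do not support a general claim about treated bone metastases, a material threat to the primary analysis, or a known net bias of bone against the other regions. The bone rule should still be reconciled with the other three, because the difference is unexplained and cheap to remove.

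**What to change.** 1. In 8.3.2 b) iii)(1), add the PSA-response criterion that the plan already applies to solitary nodal and visceral disease: a solitary PET-positive bone lesion is true positive if PSA falls by more than 50% after targeted treatment to that lesion. If the sponsor prefers to leave bone without it, state why.
2. Keep the residual false-positive default in iii)(2) for the main analysis. Do not exclude treated lesions that meet no criterion.
3. Report a sensitivity analysis of the bone, all-region and per-patient PPV with treated PET-only bone lesions that meet no criterion counted (a) as false positive, (b) as true positive, and (c) excluded. Also show the PPV without the new PSA route.

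The cost is analysis-plan wording and a few extra table rows. The PSA and treatment data are already needed for the other lesion types. The downside is that a PSA fall is not specific to a lesion, for example under concurrent systemic therapy, so a few true false positives may be upgraded. Showing the result without the PSA route makes that visible.

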8.3.2 Analysis of Primary Endpoints

PPVs on a per-patient and per-region-basis of ⁶⁸Ga-PSMA-11 PET for detection of tumor location confirmed by histopathology/biopsy will be calculated and reported along with the corresponding two-sided 95% confidence intervals. The confidence intervals will be constructed using the Wilson score method.

a) Imaging interpretation ⁶⁸Ga-PSMA-11 PET:

PET images will initially be interpreted by a board certified nuclear medicine physician or a board certified radiologist experienced in reading PET at the time of the imaging study at the institution that the study is being performed. These interpretations will not be used for final evaluation. For the data sets included in the analysis for the Primary Endpoint, imaging data will be anonymized and collected at a central site. PET data will be interpreted by three different readers in a random order at separate reading sessions. ⁶⁸Ga-PSMA PET/CT reading training set and guides will be provided and completion of this training will be required for all central review readers.

Visual interpretation:

Regions of suspected disease will be graded on a two-point scale by each reader (0=Negative or 1= Positive). A region will be judged as positive if at least one lesion in this region is visually positive.

- i) Lymph nodes will be considered positive if the ^{68}Ga -PSMA-11 uptake is focal and greater than blood pool (adjacent or mediastinal blood pool). Pelvic lymph nodes will be subclassified according to their localization as follows: R/L obturator, R/L external iliac, R/L internal iliac and other (total of 7 subgroups).
 - ii) Visceral lesions will be considered positive if the ^{68}Ga -PSMA-11 uptake is focal and greater than physiologic background activity of the involvement organ or anatomic site.
 - iii) Bone lesions will be considered positive if the ^{68}Ga -PSMA-11 uptake is focal and greater than physiologic bone marrow.
 - iv) Prostate bed and prostate lesions will be considered positive if the ^{68}Ga -PSMA-11 uptake is focal and greater than physiologic background activity of the involvement organ or anatomic site.
- b) Follow-up Imaging:

All patients will be followed up 3-12 months with conventional imaging (dedicated CT, MRI and/or bone scan). Interpretation of follow-up imaging will be performed by local read. The follow-up conventional imaging should be the same modality/modalities as the initial staging work-up to allow for reproducible and accurate comparisons.

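### In the secondary composite PPV, visceral and prostate-bed lesions are confirmed by size change without the 3 mm minimum set for nodes, and the prostate-bed true-positive window lacks the 3-month lower bound

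*Combined protocol and SAP*

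**What the plan says.** Section 8.3.2 b) classifies PET-positive findings by follow-up imaging, with separate rules by lesion type.

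- **Lymph nodes, i)(1).** True positive on more than 30% shrinkage under treatment, or on "increase by more than 20% in short axis diameter (with a minimum of 3 mm in change in size").
- **Visceral lesions, ii)(1).** The bullet begins "If on follow-up imaging within 3-12 months, visceral lesions seen on CT or MRI decrease by 30" per cent. The decrease counts only "for patients undergoing systemic treatment of focal therapy at this site"; the alternative is "increase by 20% in largest diameter". There is no minimum in millimetres.
- **Prostate bed and prostate, iv)(1).** The bullet begins "If on follow-up imaging within 12 months, lesions seen on CT or MRI decrease by 30" per cent, with the same treatment condition and growth threshold. There is no minimum in millimetres and no lower bound on time.
- **Prostate bed, iv)(2), false positive.** The size-based bullet begins "If on follow-up imaging within 3-12 months, sites of initial" and goes on to name PSMA-positive lymph node lesions. A second bullet, also worded for lymph nodes, makes anything meeting no criterion a false positive and sets no window. The visceral false-positive bullets have the same wording.
- **General schedule, b).** "All patients will be followed up 3-12 months with conventional imaging", read locally, with the same modality as at baseline.

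Sections 8.3.1 and 8.3.2 base the primary PPV on histopathology. Follow-up imaging enters the composite PPV in Section 8.3.3. Table 1 in Section 2.1 places extrapelvic nodes and organ metastases together in Region 3.

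**The concern.** The plan uses one pair of percentages for all three soft-tissue lesion types but protects only nodes against small absolute changes, and gives no reason for the difference. A 2 mm change in a 10 mm lesion confirms cancer in an organ or the prostate bed but not in a node. Region 3 then reports one PPV built on two confirmation standards.

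The prostate-bed window adds a smaller imbalance. Early growth, or early shrinkage under treatment, can count as true positive, while the size-based false-positive bullet starts at 3 months.

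At stake is the credibility of the composite PPV. Section 8.2.1 expects only about 25% of patients to have a biopsy, so this endpoint leans on the imaging rules, and it puts 30% of disease in the prostate bed.

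**Working it through.** **Plan's own figures.** The plan gives no lesion sizes and no measurement error, so there is no stated figure on this point to reproduce. The sample-size calculation in Section 8.2.1 concerns the histopathology PPV and is not at issue. By the normal approximation it gives n = ((2.326 × 0.5 + 1.282 × 0.458)/0.2)² = 76.6, against the stated 75.

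**1. Where the minimum matters.** I read the node minimum as covering increase and decrease alike, since it refers to change in size. It exceeds the percentage rule below 3/0.20 = 15 mm for growth and below 3/0.30 = 10 mm for shrinkage. A 20% increase is 1.2 mm at 6 mm, 1.6 mm at 8 mm and 2 mm at 10 mm. At 15 mm and above the minimum changes nothing.

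**2. Unchanged lesion called grown.** Let baseline B and follow-up F be independent normal measurements with the same mean d and single-measurement SD s (assumed 0.75-1.5 mm).

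- Without the minimum: P(F ≥ 1.2B) = 1 − Φ(0.2d / (s√(1 + 1.2²))) = 1 − Φ(0.2d / 1.562s).
- With the minimum, for these sizes: P(F − B ≥ 3) = 1 − Φ(3 / (s√2)).

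| True diameter | s = 0.75 | s = 1.0 | s = 1.5 |
|---|---|---|---|
| 6 mm, no minimum | 15.3% | 22.1% | 30.4% |
| 8 mm, no minimum | 8.6% | 15.3% | 24.7% |
| 10 mm, no minimum | 4.4% | 10.0% | 19.7% |
| 6, 8 or 10 mm, 3 mm minimum | 0.2% | 1.7% | 7.9% |

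In treated patients, where a 30% decrease also counts, the 6 mm figures are 17.7%, 29.1% and 46.7% without the minimum and 0.5%, 3.4% and 15.7% with it.

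**3. Lesions that truly grow.** Take an 8 mm lesion that grows 30%, to 10.4 mm.

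- Without the minimum: Φ((10.4 − 1.2 × 8) / 1.562s) = Φ(0.8 / 1.562s), which is 75.3% at s = 0.75 and 63.4% at s = 1.5.
- With the minimum: Φ((2.4 − 3) / 1.414s), which is 28.6% and 38.9%.

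**4. Net effect on PPV.** Suppose half of the PET-positive lesions are cancer, all lesions are 8 mm at baseline, and the non-cancers are unchanged.

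- If every cancer is counted: 50% + 0.5 × 8.6% = 54.3% and 50% + 0.5 × 24.7% = 62.4% without the minimum; 50% + 0.5 × 0.2% = 50.1% and 50% + 0.5 × 7.9% = 54.0% with it.
- If each cancer grows 30% and is judged by size alone, with failures defaulting to false positive: 0.5 × 75.3% + 0.5 × 8.6% = 42% and 0.5 × 63.4% + 0.5 × 24.7% = 44% without the minimum; 0.5 × 28.6% + 0.5 × 0.2% = 14% and 0.5 × 38.9% + 0.5 × 7.9% = 23% with it.

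The rule without the minimum always gives the higher PPV of the two. Against the true 50% it can lie above or below.

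**5. Prostate-bed window, for a scan before 3 months.**

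| Change seen | Size-based true-positive bullet | Size-based false-positive bullet |
|---|---|---|
| Growth of 20% | applies | never applies to growth |
| Decrease of 30%, treated | applies | does not apply (treated) |
| Decrease above 30%, untreated | does not apply | not yet open |

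The third case falls to the default false-positive bullet, if that bullet is read as covering the prostate bed.

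**The case against.** The case on the other side has real force.

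- **Endpoint.** The rules sit under the heading for the primary analysis, so a reader might infer that the powered test of 50% against 70% is affected. It is not: that PPV rests on histopathology. After a negative biopsy, the plan sends cases to the follow-up imaging rules only for nodes and bone. A general clause allows repeat imaging after any negative biopsy but sets no size criterion. This stands.
- **Direction.** A reader might infer that measurement noise inflates the PPV. Step 4 shows that this does not follow, because a hard minimum also loses lesions that truly grow. This stands, and it is why the 3 mm rule should not simply turn these lesions into false positives.
- **Size.** SD and lesion diameters are assumed, and the 46.7% figure is an extreme corner. Same-modality follow-up should limit error. A prostate-bed or solitary visceral lesion unchanged after targeted treatment is already true positive if PSA falls by more than 50%, so noise cannot alter that verdict. This stands.
- **Window.** The general rule already schedules imaging at 3-12 months, so an earlier scan is off schedule, and the bone rules also use an open 12-month window. This limits the practical effect but does not remove the mismatch within the prostate-bed rules.
- **Intent.** Nodes are measured on the short axis and the others on the largest diameter, so the difference may be deliberate. The plan does not say so, and diameter type alone does not explain why 2 mm suffices in one and not the other.

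**Conclusion.** The point holds for the secondary composite PPV only. For lesions under 15 mm (growth) or under 10 mm (treated shrinkage), the visceral and prostate-bed rules accept changes that the node rule rejects, and Region 3 mixes the two standards. On an assumed single-measurement SD of 0.75-1.5 mm, an unchanged 6-10 mm lesion is called grown in about 4-30% of cases, against 0.2-8% with the minimum. The composite PPV is therefore equal to or higher than it would be under the node rule. The documents do not support saying that it is too high against the truth. The effect per region or per patient cannot be derived, since the share of small lesions is not given.

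The prostate-bed window is a separate, smaller inconsistency: early growth or early treated shrinkage can count only towards a true positive.

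A related drafting fault needs correcting at the same time. Read literally, the false-positive bullets under visceral and prostate-bed lesions cover only lymph nodes, which leaves those two lesion types with no false-positive rule.

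**What to change.** 1. In 8.3.2 b) iv)(1), reconcile the window with the plan's general follow-up rule of 3-12 months.
2. For visceral and prostate-bed lesions, label a change that passes the percentage but is under 3 mm as *unconfirmed by size*, not as false positive. Apply the same minimum to the size-based false-positive bullets in ii)(2) and iv)(2), so that a small untreated decrease is handled in the same way. State whether such a lesion counts as unchanged for the PSA-based criterion.
3. Report the composite PPV, per patient and per region, with these lesions classified as the plan now has it and again with them left out of numerator and denominator.
4. Reword the false-positive bullets in ii)(2) and iv)(2) to name the lesion type that they sit under.

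This is a change of wording plus one extra tabulation, using diameters that the size rules already require. The downside is that fewer small lesions are confirmed by size, so in the second analysis the composite PPV may be lower and less precise.

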3.3.2 Exclusion Criteria

1. Investigational therapy for prostate cancer.
2. Unable to lie flat, still or tolerate a PET scan.
3. Prior history of any other malignancy within the last 2 years, other than skin basal cell or cutaneous superficial squamous cell carcinoma that has not metastasized and superficial bladder cancer.
4. Contraindication to furosemide administration including prior allergy or adverse reaction to furosemide or sulfa drugs. (Note: This exclusion criteria can be removed if Furosemide is omitted as part of the PET imaging protocol if a second-generation scatter correction is available for the used PET device).

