6.2 Prohibited Medications

There are no prohibited medications.

7 Reporting and Documentation of Results

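### The PSA-fall rule for prostate-bed lesions lacks the solitary-disease limit of the node and visceral rules, so it can raise the secondary composite PPV

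*Combined protocol and SAP*

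**What the plan says.** Section 8.3.2 b) sets out how PET-positive lesions are validated on follow-up. Three of its four lesion types have a rule under which a fall in PSA makes a lesion a true positive:

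- Lymph nodes, b) i): "If patients with solitary lymph node regions show a decrease of PSA by greater than 50% after targeted treatment", with the node stable in size.
- Visceral lesions, b) ii): "If patients with solitary visceral metastasis show a decrease of PSA by greater than 50% after targeted treatment", with the lesion stable in size.
- Prostate bed and prostate, b) iv): "If patients with prostate bed lesions show a decrease of PSA by greater than 50% after targeted treatment" "and lesions do not change in size (less than 30% decrease or 20% increase in largest diameter").

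The first two are limited to solitary disease and the third is not. The size-change rule just above the bed PSA rule foresees both systemic and site-directed therapy ("for patients undergoing systemic treatment of focal therapy at this site"). The PSA rule does not say that the targeted treatment went to the bed, or to the bed alone.

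Elsewhere, section 6.2 states "There are no prohibited medications", and the only treatment-based exclusion in section 3.3.2 is "Investigational therapy for prostate cancer". The follow-up rules feed the secondary composite PPV of section 8.3.3, which combines histology with imaging follow-up. By sections 8.3.1 and 8.3.2, the primary PPV rests on histology.

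**The concern.** PSA is a whole-patient marker. When several sites are PET-positive, a fall after treatment does not show which site held tumor. The solitary limit in the node and visceral rules deals with this problem, which exists equally in the bed, and the plan gives no reason for leaving the limit out there.

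The bed PSA rule operates only when the lesion has not changed in size, so the fall in PSA is then the only follow-up evidence. If the bed uptake was false and the fall came from treating disease elsewhere, the lesion is recorded as a true positive.

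The composite endpoint matters in practice. Section 8.2.1 expects about 25% of patients to have a biopsy, so 1,500 − 375 = 1,125 would depend on follow-up for any confirmation. The bed is the second largest region there, at 30%.

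**Working it through.** **The plan's own figures.** The plan states no figure for the PSA rule. The nearest is the 98% power for the prostate bed in section 8.2.1 (PPV 50% against 70%, n = 113, one-sided 0.01). It reproduces: Φ((0.20 − 2.326·√(0.25/113)) / √(0.21/113)) = Φ(2.10) = 98.2%. That figure belongs to the primary, biopsy-based test. Section 8.3.3 plans confidence intervals and McNemar comparisons for the composite, not a test against 50%, so the power figure is not used further.

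**The three rules compared.**

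| Condition | Nodes | Visceral | Bed |
|---|---|---|---|
| PSA fall above 50% | yes | yes | yes |
| After targeted treatment | yes | yes | yes |
| Size unchanged | yes | yes | yes |
| Solitary disease | yes | yes | **no** |
| Concurrent systemic therapy excluded | no | no | no |

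Only the fourth row is specific to the bed. The last row is common to all three rules.

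**Example.** A patient has PET-positive uptake in the bed and in a pelvic node. Targeted treatment is given, PSA falls by more than 50%, and neither lesion changes in size. The bed lesion is confirmed. If solitary means the only positive site, the same fall in PSA cannot confirm the node.

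**Size of the effect.** Let p be the true PPV among PET-positive bed lesions. Let c be the share of bed false positives re-labelled by the rule. The documents do not give c, so it is an assumption. If every true lesion is confirmed by some route:

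reported PPV = p + (1 − p)c

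| c | p = 50% | p = 60% |
|---|---|---|
| 10% | 55% | 64% |
| 20% | 60% | 68% |
| 30% | 65% | 72% |

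**Error in the other direction.** Suppose a share u of true bed lesions stays unconfirmed and is counted as false positive. Then reported PPV = p(1 − u) + (1 − p)c. The two errors cancel when pu = (1 − p)c. For p = 50% this means u = c: with both at 20%, 0.50 × 0.80 + 0.50 × 0.20 = 50%.

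**Effect of removing PSA-confirmed lesions.** If the lesions removed are a share t of the true ones and c of the false ones:

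PPV = p(1 − t) / [p(1 − t) + (1 − p)(1 − c)]

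With assumed p = 0.60, t = 0.40, c = 0.20: 0.36 / (0.36 + 0.32) = 0.53. With the same p and c, the current rule reports 0.60 + 0.40 × 0.20 = 0.68. Here the two versions lie on either side of the true 0.60. This happens whenever t exceeds c.

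**The case against.** The strongest reply is that the rule is narrower than it first looks and serves a purpose. It needs targeted treatment, a PSA fall above 50% and stable size, all together. It also confirms genuine bed recurrences that stay the same size after treatment, which would otherwise fail the size criterion. The default for unconfirmed bed lesions is itself unclear, because the false-positive bullet under the bed heading is worded for nodes ("positive lymph node lesions do not meet the criteria for above false positive or true positive findings"). If that default is meant for bed lesions, dropping the PSA rule would turn some real recurrences into false positives. All of this stands. It limits the claim and argues for restricting the rule rather than deleting it.

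The benchmark can also be questioned. A solitary lymph node region may mean one nodal region rather than no other positive site. That reading is possible, and the plan should settle it. Either way, the bed rule has no limit at all.

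A reader might infer more than the text supports:

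- *Systemic therapy alone confirms a bed lesion.* It does not, because targeted treatment is also required. The gap is systemic therapy given alongside it, and all three PSA rules share that gap.
- *The documents show how often this happens.* They show that systemic treatment is foreseen and not prohibited. They give no frequency for the joint event behind c.
- *The regional results lose their comparability.* Section 8.3 plans no comparison between regions, and the criteria already differ by region, for instance for bone.

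**Conclusion.** The point holds as a gap in the secondary reference standard. As written, the bed rule can label a false-positive lesion true positive when PSA falls because other disease was treated. Through that route it can raise the composite PPV for the bed region and per patient.

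The size is unknown. The move from 50% to between 55% and 65% rests on an assumed c of 10% to 30% and on all true lesions being confirmed. A reader might conclude that the composite PPV is certainly biased upward. The documents do not establish that, since true lesions left unconfirmed pull the other way. Nor is the primary PPV touched: it rests on histology, and section 8.3.2 c) sends negative node and bone biopsies to the follow-up rules but gives no such route for the bed.

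This is a cheap improvement, best settled before lesions are classified, so that it cannot be seen as driven by results.

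**What to change.** Change the classification wording in section 8.3.2 b) iv) and add analyses to section 8.3.3:

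1. Limit the bed PSA rule to patients in whom the bed is the only PET-positive region, and state what solitary means in the node and visceral rules.
2. Classify size-stable bed lesions outside that limit by histology where available and otherwise as not evaluable, and report their number. Reword the false-positive default under the bed heading so that it refers to bed lesions and agrees with this.
3. Add a sensitivity analysis of the composite PPV that omits every lesion confirmed by PSA fall alone.
4. Add a second one that omits PSA-confirmed lesions with concurrent systemic therapy, across all three PSA rules. This is preferable to barring such lesions in the main rule, which could remove true lesions and lower the PPV.

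The cost is plan wording, a record of systemic therapy for PSA-confirmed lesions, and two extra analyses. There will be fewer evaluable bed lesions, some of them true, so precision falls and the PPV could shift downward. Reporting the main and sensitivity results side by side makes that visible.
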